## **6. SAMPLE SIZE DETERMINATION**

### **6.1 Primary Outcome**

The risk of preterm birth < 37 weeks gestation in untreated nulliparous women was estimated to be about 8.0% for the EAGeR trial (Abramovitch, 2012 and Schusterman, 2014). Unpublished data for 2012 from the GN sites shows preterm birth rates, ranging from 2.9% to 9.8%, while WHO estimates the range for the countries in which GN sites are located to be 7.7% to 16.7% 1. In developing sample size estimates we considered risks in the range of 8% to 14% and ultimately selected sample sizes based on a conservative estimate of 8%. Because the association of LDA and preterm birth may differ in international settings, we examined sample size requirements for reductions of 40%, 25%, and 20%. As shown in the protocol, the number of evaluable participants needed to detect a 20% reduction from a usual rate of 8% preterm births with 90% power is 5,483 per treatment arm. To account for the loss of evaluable subjects due to miscarriages, which are anticipated to occur in approximately 5% of participants) and loss to follow-up (assumed to be in the 1% to 2% range), sample sizes were increased by 8% to obtain a final sample size of 11,920 (or 5,960 per treatment arm).

### **6.2 Secondary Outcomes**

One of the key secondary objectives of this trial is to evaluate the effect of low dose aspirin on perinatal mortality. We evaluated the reduction in perinatal mortality that could be detected with 80% power and 90% power under the assumption that the sample size for the study would be based

on that needed to achieve the primary aim of demonstrating a 20% reduction in low-birth weight infants. The analyses were based on the assumption that the perinatal mortality rate in the GN population is approximately 45 perinatal deaths per 1000 deliveries (unpublished data from the MNH Registry for 2013). With this estimated underlying mortality rate and 5,483 evaluable subjects per treatment arm required to demonstrate the 20% reduction in low birth weight prevalence as outlined in the primary aim, the study will have 80% power to detect a 24% reduction in perinatal mortality and 90% power to detect a 27% reduction in perinatal mortality.

To determine the sample size actually needed to demonstrate the reduction in perinatal mortality actually expected if the intervention results in a 20% reduction in prevalence of low birth weight infants, we examined both the prevalence of low birth weight infants across the GN sites and the perinatal mortality risk in both the low birth weight and normal birth weight infants. Based on 2013 MNH Registry data, the prevalence of low birth weight among all GN deliveries was 16.3% and the perinatal mortality rates were 20.5 per 1000 deliveries among normal birth weight infants and 162.3 per 1000 deliveries among low birth weight infants; these values yield a weighted average perinatal mortality rate of 43.6 per 1000 deliveries. If the low dose aspirin intervention is effective in reducing the prevalence of low birth weight deliveries by 20% (i.e. reducing the prevalence from 16.3% to 13%) and the conditional risk of perinatal mortality is unchanged in the low birth weight and normal birth weight cohorts, we would expect the resultant overall perinatal mortality rate to be reduced to 38.9 per 1000 deliveries or a 10.8% reduction. Detection of a reduction of this magnitude with 80% power would require an evaluable sample size of greater than 28,000 evaluable deliveries per treatment arm, and the study would need over 37,000 evaluable deliveries per arm to achieve 90% power to detect a reduction of this level in perinatal mortality.

Given the sample sizes associated with the second approach, the best alternative appears to be to power the study to demonstrate the 20% reduction in prevalence of low birth weight deliveries with a commitment to generate point and interval estimates of the impact of the intervention on perinatal mortality. By examining the risk of perinatal mortality in both the normal and low birth weight infants in the two arms, the trial would provide some insight about impacts of the intervention on mortality other than that mediated through the effect on birth weight.

We also conducted power analyses to examine the effect sizes that could be detected with the planned sample sizes for two additional secondary outcomes, prevalence of SGA infants and incidence of eclampsia/preeclampsia in the target population. Generic information as well as preliminary information from the 2013 MNH Registry indicates that the risk of each of these events in the population of interest is approximately 5%. Under the assumption of 5483 evaluable participants in each treatment arm and an assumed Type I error rate of 0.05 for per-comparison analyses (i.e. no control for multiple comparisons in the analyses of these secondary outcomes), the study will have 70% power to detect a 20% reduction in the risk of each of these outcome measures, 85% power to detect a 24% reduction and 90% power to detect a 26% reduction. Consequently, the study is reasonably powered to examine these secondary outcome measures.

## **7. STATISTICAL / ANALYTICAL ISSUES**

### **7.1 General Rules**

All statistical computations will be performed and data summaries will be created using SAS 9.3 or higher. If additional statistical packages are required, these will be discussed in the study report. For summaries of study data, categorical measures will be summarized in tables listing the frequency and the percentage of participants in each study arm; continuous data will be summarized by presenting

mean, standard deviation, median, minimum, and maximum; and ordinal data will be summarized by only presenting median and the limits of the interquartile range.

## **7.2 Adjustments for Covariates**

As this is a randomized trial and the randomization process was not compromised during execution, the treatment effect estimate from trial is unbiased, even without adjusting for any baseline covariates. Therefore, no adjustments for covariates other than site are planned for the primary analysis. However, baseline clinical and demographic variables that are known predictors of neonatal mortality and maternal outcomes will be included in secondary analyses of intervention efficacy.

## **7.3 Missing Data Approaches:**

The study is likely to have two primary sources of missing data. Since the primary interest is in delivery outcomes for women who deliver after 20 weeks, the first primary source for missing data is early pregnancy losses due to miscarriage or medical termination of pregnancy (MTP) prior to 20 weeks gestational age. The second primary reason for missing data will be participant loss to follow-up. Each of these scenarios is treated separately below.

Women are being enrolled in the ASPIRIN trial when they are between 6 0/7 weeks and 13 6/7 weeks gestational age. Depending on the distribution of study participants over this gestational age range we anticipate that between 2% and 8% of the women in the study will have a pregnancy loss prior to 20 weeks. For the primary outcome of preterm birth, these women will be excluded from the analyses and hence be considered missing at random. However, because we recognize that these women may not have the same risk of preterm delivery as those followed past 20 weeks, we will generate two additional sensitivity analyses to assess whether inference is robust to this assumption. For the first analyses, these early terminations will be treated as preterm deliveries in a full ITT analysis. For the second approach, the MITT population will be used with inverse probability weighting used to account for the individuals lost prior to 20 weeks.

Based on the historical data available from the MNH registry, we anticipate that the rate of missing responses for maternal and neonatal morbidity and mortality measures are likely to be 2% or less. Although we do not expect this rate to change over the course of this trial, we will examine data from both arms to ensure that the missing rate is comparable in the participants assigned to the Aspirin and Placebo treatment arms. We will examine patterns of missing data by arm and site. If more than 2% of data in either or both arms are missing, we will conduct sensitivity analysis on the effect of the missing on the inference by using use multiple imputation procedures. Multiple imputation assumes that the mechanism that caused the missing is independent of the value of the unobserved data (i.e. data are missing at random – MAR). Although there is no reason to believe that the missing data on the use would not be MAR, multiple imputation processes have been shown to be robust even if the missing mechanism is dependent on the values of the unobserved data, i.e. even if the missing data are non-ignorable non-response. The results of all sensitivity analyses will be presented in the final report.

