### Intention to Treat (ITT) Population

The intention to treat population will include all eligible, randomized participants. All participants will be assigned to the arm to which they were randomized irrespective of treatment received. Unless specified otherwise, all participants will be included in analyses using this population (with data imputed as needed and irrespective of protocol deviation occurrence, subsequent study participation termination, or study drug withdrawal). This population will be used to conduct sensitivity analyses for the primary outcome.

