## **7.5 Multiple Comparisons and Multiplicity**

There is only one formal hypothesis test for this study. As such, a statistical test will be conducted at a 5% type I error rate (two-sided) for the primary efficacy measure, and no adjustments for multiplicity will be made. All analyses of secondary outcomes are exploratory in nature; therefore, p-values and confidence intervals are provided for descriptive purposes only. All p-values provided for any baseline and demographic characteristics and safety parameters will be for descriptive purposes only. As such, unless otherwise specified, p-values presented will be on a per analysis basis, with no further control for multiple tests.

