# **8. STUDY PARTICIPANTS, TREATMENT EXPOSURE AND COMPLIANCE**

## **8.1 Participant Disposition**

Participant eligibility status will be summarized by study arm and overall disposition of study participants will be described using a standard CONSORT diagram. The number of participants randomized; completing or discontinuing from study therapy; and completing the study follow-up will be summarized by study arm. Reasons for study withdrawal will also be summarized by treatment arm to assess whether they are balanced across treatment arm and to assure that any imbalances are unlikely to affect inference.

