## 9.4 Primary Analysis

The primary analysis will compare the risk of preterm birth between the two treatment arms using two complementary approaches. First, the formal test of the primary hypothesis that the risk of preterm birth differs between the two arms will utilize a modified intention-to-treat approach based on a Cochran-Mantel-Haenszel test stratified by Global Network sites. The approach is characterized as a modified intention to treat approach because the analysis population for the test will be all randomized pregnancies for which the delivery occurs after 20 weeks. Earlier deliveries (miscarriages) will be considered missing completely at random for purposes of this analysis.

In order to evaluate the sensitivity of the primary hypothesis test to the assumption by which miscarriages are treated as randomly missing and to control for potential confounders of the treatment effect, additional analyses will be conducted using a series of three generalized linear models. These generalized linear models will be fit with the binary outcome of preterm (<37-week delivery) as the outcome measure. The initial model will include terms for treatment, site, and a treatment by site interaction. If the treatment by site interaction term is found to be significant ( $p<0.05$ ), then all subsequent models will include the interaction term and all effects will also be reported by site, although formal inference will be based on the average effect across sites. If the interaction term is not significant, it will be removed from the model and this initial model be used to estimate an unadjusted treatment effect controlling for site. The second series of models will include any demographic or clinical variable found to differ significantly between the treatment arms in the preliminary analyses described above. These models will be used to generate adjusted estimates of the treatment effect controlling for potential confounders. The third set of models will utilize extensions of the generalized linear model that incorporate inverse probability weighting to evaluate the sensitivity of the inference to treatment of miscarriages as randomly missing (Hogan, 2004). As described in Section 7.3, we will also conduct sensitivity analyses using the full ITT population; for these analyses, missing data due to loss to follow-up will be handled using multiple imputation, and these early terminations will be treated as preterm deliveries.

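### SAP 7.3 wrongly treats multiple imputation as robust to non-ignorable missingness, so loss to follow-up is examined only under missing at random

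*Combined protocol and SAP*

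**What the plan says.** SAP 7.3 separates two sources of missing data. Losses before 20 weeks get two sensitivity analyses: counted as preterm in a full ITT analysis, and inverse probability weighting in the mITT population. For loss to follow-up the tool is MI, under a condition: "If more than 2% of data in either or both arms are missing, we will conduct sensitivity analysis". The section gives the assumption correctly, "Multiple imputation assumes that the mechanism that caused the missing is independent of the value of the unobserved data", and then says without a citation that "multiple imputation processes have been shown to be robust even if the missing mechanism is dependent on the values of the unobserved data".

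SAP 9.4 adds an ITT sensitivity analysis of preterm birth in which "missing data due to loss to follow-up will be handled using multiple imputation, and these early terminations will be treated as preterm deliveries". The ITT definition in SAP 5 agrees: "all participants will be included in analyses using this population (with data imputed as needed". The other provisions are descriptive. SAP 7.3 compares missing rates and patterns by arm and site, and in SAP 8.1 "Reasons for study withdrawal will also be summarized by treatment arm to assess whether they are balanced across treatment arm".

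**The concern.** The two sentences in 7.3 contradict each other, and the second is wrong. Standard MI fills in a lost woman's outcome from women who look like her in the observed data. If her risk differs given those data, the imputed values are biased, unless the imputation model builds the difference in. The SAP specifies no such model.

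The sentence matters because it stands where an analysis should be. The SAP doubts MAR for losses before 20 weeks and tests it there, but for loss to follow-up it offers this assurance. The MI run in 9.4 does not fill the gap. It imputes under MAR and, in the same analysis, counts every loss before 20 weeks as preterm, so a change in the result could not be attributed to loss to follow-up. The SAP also leaves open whether the 2% condition in 7.3 applies to the unconditional MI in 9.4.

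At stake is whether a moderate or borderline primary result can be defended if loss is informative and differs between arms.

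**Working it through.** **Inputs.** Placebo risk 8%, 20% reduction (6.4%), 90% power, 5,483 evaluable and 5,960 randomized per arm, about 5% miscarriage and 1-2% loss to follow-up (SAP 6.1). Two-sided 5% test (SAP 7.5). A pooled two-proportion z-test stands in for the site-stratified CMH test.

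**1. The plan's own figure.** n = [1.960·√(2·0.072·0.928) + 1.282·√(0.08·0.92 + 0.064·0.936)]² / 0.016² = 5,483 per arm, and 5,483/0.92 = 5,960. Both reproduce.

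**2. How much is missing.** Women reaching 20 weeks: 5,960 × 0.95 = 5,662 per arm. Loss of 1-2% is 57-113 women per arm, with about 5-9 expected preterm births at 8% risk.

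**3. Tipping point.** Hold missing placebo women at 8%, so the placebo total stays at 8.0%. With N = 5,662 per arm, z = 1.96 when the aspirin total reaches 7.03%:

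(0.0800 − 0.0703) / √(0.0751 × 0.9249 × 2/5,662) = 0.0097/0.00495 = 1.96.

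If a fraction L of aspirin women is lost and the observed aspirin risk is p, the tipping risk among them is r = [0.0703 − (1 − L)p]/L. For L = 0.02 and p = 0.064, r = (0.07029 − 0.06272)/0.02 = 37.8%.

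| Observed aspirin risk (placebo 8.0%) | 1% loss | 2% loss | 4% aspirin, 2% placebo (assumed) |
|---|---|---|---|
| 6.4% (design effect) | 69.3% | 37.8% | 22.1% |
| 6.6% | 49.5% | 28.0% | 17.3% |
| 6.8% | 29.7% | 18.2% | 12.5% |

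With N = 5,483 the rows become 67.8/37.1/21.7%, 48.0/27.3/16.9% and 28.2/17.5/12.1%.

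**4. A second set-up.** Take 5,483 observed women per arm plus 119 missing (2% of 5,960), and add aspirin events until p exceeds 0.05.

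| Observed RR | Observed p | Tipping events | Tipping risk |
|---|---|---|---|
| 0.87 | 0.039 | 12/119 | 10.1% |
| 0.86 | 0.025 | 17/119 | 14.3% |
| 0.85 | 0.016 | 21/119 | 17.6% |
| 0.84 | 0.010 | 26/119 | 21.8% |
| 0.80 | 0.0012 | 43/119 | 36.1% |

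**5. Would MAR imputation show this?** No. Filling in the 119 per arm at each arm's observed risk moves p only from 0.039 to 0.036 at RR 0.87 and from 0.0012 to 0.0011 at RR 0.80. This uses expected counts and ignores between-imputation variance.

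**6. Informative loss equal in both arms.** N = 5,662, 2% loss, 8.0% vs 6.4%: z = 3.22 with missing women in both arms at 8% risk, and 3.10 with both at 40%.

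**7. What the 9.4 ITT run does.** At 5% early loss, 298 women per arm are counted preterm. For 8.0% vs 6.8% with no loss to follow-up, mITT 453/5,662 vs 385/5,662 gives z = 2.44 (p = 0.015). ITT (298 + 453)/5,960 vs (298 + 385)/5,960 = 12.6% vs 11.5% gives z = 1.91 (p = 0.056). The 298 recoded events per arm swamp the 5-9 expected among lost women.

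**The case against.** The strongest reply is that the practical effect is small. At the loss the SAP expects, overturning the design effect needs a preterm risk in missing aspirin women of about 4.6 to 8.7 times that in missing placebo women (37/8 to 69/8). Any result near 0.05 is fragile to almost any perturbation. The departure must also differ by arm, and the trial is double-blind with an identical-appearing placebo. Outcomes come from the established MNH Registry, so a woman who stops her pills need not have a missing delivery date. The 4% vs 2% case has no support in the documents, and the planned comparison of missing rates by arm would show such an imbalance.

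These points stand as limits on importance. They do not make the sentence true or supply the missing analysis. Describing rates and reasons by arm does not show how the effect estimate would change, and loss above 2% triggers only more MI under MAR.

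Two further points are fair. The 2% condition follows a sentence about maternal and neonatal morbidity and mortality measures, so the natural reading is that 9.4 governs preterm birth; one clarifying sentence settles that. And the ITT calculation in step 7 measures dilution by recoding, not bias from informative loss. It is used here only to show that the 9.4 run cannot isolate loss to follow-up.

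**Conclusion.** The concern holds. The robustness statement in SAP 7.3 is incorrect as a general property of MI and contradicts the sentence before it. IPW and the preterm recoding cover only losses before 20 weeks, and no analysis examines the primary effect under a departure from MAR for loss to follow-up.

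The size depends on the result. At 2% loss, with missing placebo women at 8%, significance is lost at a missing-aspirin risk of about 36-38% for the full design effect, 17.5-22% for a moderate result (RR 0.84-0.85) and 10-14% for a borderline one (RR 0.86-0.87). Higher or unequal loss lowers these values. They rest on an unstratified z-test, the SAP's assumed loss rates and a departure that differs by arm. The plan should be changed, although the primary test itself is not at fault.

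**What to change.** - In SAP 7.3, delete the sentence claiming robustness to non-ignorable missingness.
- Before unmasking, pre-specify a delta-adjusted MI (tipping-point) analysis of preterm birth for women lost to follow-up. Shift the imputed log-odds separately by arm over a stated grid, for example −1 to +3.5 in steps of 0.5. A shift of +3.5 takes 6.4% to 69%, which covers the tipping values above. Report where the site-stratified CMH result crosses 0.05.
- Keep this analysis apart from the recoding of losses before 20 weeks, and run it whatever the missing rate.
- State in 7.3 that the 2% trigger does not govern the primary-outcome analyses in 9.4.

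The wide grid includes implausible shifts. Reporting the crossing line lets readers judge which part of it is credible.

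The cost is one deleted sentence, one clarifying sentence, a short extra program on the imputed data sets and one more sensitivity table. No new data are needed and the primary test is unchanged.

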## **7.4 Multicenter Studies**

For this multicenter study, randomization of study participants was stratified within site. Consequently, for all test-based analyses of treatment effect and model-based primary and secondary analyses, site will be included as a fixed effect in the models. As an ancillary analysis associated with the primary outcome (risk of premature delivery) as well as secondary outcomes, we will examine

descriptively whether the treatment effects vary across sites; however, these analyses of site differences in treatment effect are considered to be descriptive because sample sizes are likely inadequate to provide adequate power to detect site by treatment interaction effects.

## **7.5 Multiple Comparisons and Multiplicity**

There is only one formal hypothesis test for this study. As such, a statistical test will be conducted at a 5% type I error rate (two-sided) for the primary efficacy measure, and no adjustments for multiplicity will be made. All analyses of secondary outcomes are exploratory in nature; therefore, p-values and confidence intervals are provided for descriptive purposes only. All p-values provided for any baseline and demographic characteristics and safety parameters will be for descriptive purposes only. As such, unless otherwise specified, p-values presented will be on a per analysis basis, with no further control for multiple tests.

## **7.6 Masked Data Review**

A masked data review process will be performed by members of the protocol team prior to final data lock to define study analysis populations and to adjudicate key outcome variables. Key questions that will be addressed during this review will be definition of individuals to be included in the per protocol population, adjudication of the primary outcome variable and selected secondary outcomes for this study. Detailed documentation of the masked data review and resulting decisions will be described in a SAP addendum.

# **8. STUDY PARTICIPANTS, TREATMENT EXPOSURE AND COMPLIANCE**

## **8.1 Participant Disposition**

Participant eligibility status will be summarized by study arm and overall disposition of study participants will be described using a standard CONSORT diagram. The number of participants randomized; completing or discontinuing from study therapy; and completing the study follow-up will be summarized by study arm. Reasons for study withdrawal will also be summarized by treatment arm to assess whether they are balanced across treatment arm and to assure that any imbalances are unlikely to affect inference.

